## **2: STUDY AIMS AND OBJECTIVES**

### **2.1 Primary objectives and endpoints**

Primary objective	Endpoints

The primary objective is to establish a functional dose of each FDA-approved therapy for glioma in Pear Bio's ex vivo platform, and to confirm these therapies demonstrate their intended mechanism of action (direct cell killing, cell killing by immune cell activation, etc.)
	
As the primary objective is laboratory-based, a patient outcome endpoint is not necessary. Instead, success will be determined by:
 
 
1. Observing differentiated ex vivo treatment response across the therapies/combos tested on each patient's tumour sample (intra-patient sample comparison)
 
2. Observing differentiated ex vivo treatment response levels between the cohort of samples collected from patients on a per therapeutic/combo basis (inter-patient sample comparison)
 

## 2.2 Secondary objectives and endpoints

Secondary objectives	Endpoints

Assess the accuracy of Pear Bio's assay at correlating to patient progression free survival (PFS)
	
Tumour response will be measured as clinically indicated (typically every 3 months), and at all subsequent timepoints until disease progression, as per standard of care.
 
Disease progression is evaluated by the patient's radiologist and is defined by RANO guidelines.
 
Kaplan–Meier curves will be generated on the patient population, and where feasible, based on their line of treatment and for each therapeutic option (if n is sufficient). These curves will be compared to reported data to determine how representative the patient population is of past trials and clinical practice.
 
Computer vision biomarkers will be categorised into low/high groups to determine their correlation with PFS. This analysis will not demonstrate the patient benefit of using Pear Bio's tool, but it will generate hypotheses for interventional trials designed to demonstrate patient benefit.

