Various Pear Bio laboratory assays will be compared to validate cell culture models, computer vision algorithms and drug mechanisms of action. Any available patient data will also be used to determine whether Pear Bio's assays can predict patient outcomes, such as recurrence or eligibility for future targeted therapies. However, due to the variety of patients recruited, the low total sample size, and the lack of evaluable patients receiving non-surgical treatment, no formal statistical analysis will be conducted on patient outcomes.

At the end of this study, Pear Bio will determine whether the platform has potential for patient stratification in primary brain tumours. Future studies will aim to demonstrate the sensitivity/specificity of Pear Bio's platform for an eventual intended use in guiding treatment decision making for patients with primary brain tumours in order to increase their response rates.

Our Patient & Public Engagement & Involvement (PPIE) workstream will hold three meetings and use online questionnaires and consultations to help understand patient, carer, professional and public views on the Pear Bio platform and its use.

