### **1.2.1 Current management of malignant glioma**

Malignant glioma includes grade 2-4 glioma, and forms the majority of primary brain tumours in adults. Glioma therapy depends on grade and subtype but broadly includes a combination of surgical resection, radiotherapy and chemotherapy.

Optimal treatment of glioblastoma (grade 4 glioma) consists of surgery, chemo-radiotherapy and chemotherapy with Temozolomide (3). For grade 3 astrocytoma, surgery, radiotherapy and adjuvant temozolomide are standard of care (4), and for oligodendroglioma, surgery, radiotherapy and PCV-based chemotherapy are standard of care. At relapse, therapy is typically further chemotherapy, either with the same agents, or previous unused chemotherapy. 3rd-line chemotherapy is poorly defined, but might include carboplatin or irinotecan, and may include bevacizumab.

Combined TMZ & Lomustine may be beneficial in MGMT methylated GBM, but apart from MGMT methylation, IDH mutation and 1p/19q co-deletion - which predict response to chemotherapy in general - there are no biomarkers to predict response to specific therapeutic agents.

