### **5.5.5 Treatment details**

Patients will receive surgery as per standard of care. Consenting patients will have a portion of their tumour and blood used for this study.

For patients who have adjuvant therapy within the study period, the following details will be collected at each cycle: drug name, start date and end date, dose/units, dose reductions/interruptions, reasons for any treatment changes/interruptions/dose reductions, or details of radiotherapy dose, fractionation, start and end dates, and for surgery, dates and times of surgery and post-operative stay.

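### The assay-to-PFS analysis does not say which ex vivo readout is used or account for treatment received, grade or line, so an association could be prognostic only

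*Combined protocol and SAP*

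**What the plan says.** Section 2.2 gives the comparison of assay and PFS one sentence: "Computer vision biomarkers will be categorised into low/high groups to determine their correlation with PFS". It names no culture, regimen, cut-point, model or covariate. The text then disclaims any demonstration of patient benefit and says that "it will generate hypotheses for interventional trials designed to demonstrate patient benefit".

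Treatment enters the PFS plan only through Kaplan-Meier curves by line and therapeutic option, where numbers permit. Their stated purpose is a different one: "These curves will be compared to reported data to determine how representative the patient population is of past trials and clinical practice".

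Other sections do not fill the gap:
- Section 7.2.2, the secondary analysis, relates omics biomarkers to ex vivo response and contains no PFS analysis.
- Section 7.2.3 mentions predictive and prognostic biomarkers together, with no way of telling them apart.
- The OS analysis in section 2.3 deliberately disregards which therapy was given.

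On the cohort, section 4.1 admits grades 1 to 4 (2 to 3 for meningioma) and section 3.1 includes further surgery after earlier treatment. Section 1.1 does not exclude samples by subtype, and it cites "the lack of evaluable patients receiving non-surgical treatment" among its reasons for planning no formal analysis of outcomes. Section 1.2.1 ties glioma treatment to grade and subtype; for example, "Optimal treatment of glioblastoma (grade 4 glioma) consists of surgery, chemo-radiotherapy and chemotherapy with Temozolomide".

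On data, section 5.5.5 states: "For patients who have adjuvant therapy within the study period, the following details will be collected at each cycle". Section 3.3, however, lists follow-up treatment and outcome data as collected only if available.

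**The concern.** The test is meant eventually to guide the choice of regimen (section 1.3). The hypothesis worth carrying forward is therefore drug-specific: does a good ex vivo readout for a drug go with longer PFS in patients given that drug? A low/high split that ignores the drug received does not address this.

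Two things can go wrong. First, grade is tied to both prognosis and treatment, so a metric that happens to differ by grade will track PFS through natural history. Second, if the readout for one drug is compared with PFS in patients who mostly had something else, or surgery only, a real drug-specific signal shrinks towards nothing. In either case the result would be reported under an objective worded as accuracy of the assay and could steer the design of interventional trials.

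**Working it through.** The plan has no figure to reproduce. Section 7.1 gives 50 evaluable patients as a maximum, without formal power, and no effect size or event count is stated. What follows shows scale only.

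**1. Choice of readout.** Section 3.4 lists a control and five active regimens, subject to cell numbers. Section 7.2.1 lists three families of image metric. With the full standard set that is 6 × 3 = 18 candidate readouts per patient, before counting the different summaries of migration, against one PFS time. Section 2.2 does not choose among them.

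**2. Association through grade alone.** From the documents: at most 50 patients and at most 12 months of follow-up (section 7.4). Assumed: exponential PFS; median 7 months in grade 4 and 24 or 40 months in lower grades; grade 4 share 50% or 70%; a high readout in 60% of grade 4 versus 40% of lower grades, or 70% versus 30%; and no effect of the marker within grade.

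For each grade group, hazard h = ln 2 / median, event probability P = 1 − 2^(−12/median), and mean time at risk T = P/h. The rate in a marker group is the weighted sum of P over the weighted sum of T.

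Example with half grade 4, lower-grade median 24 months, and 70/30:
- Grade 4: P = 0.695, T = 7.02. Lower grade: P = 0.293, T = 10.14.
- High group (70% grade 4): (0.7 × 0.695 + 0.3 × 0.293) / (0.7 × 7.02 + 0.3 × 10.14) = 0.574 / 7.956 = 0.0722 per month.
- Low group (30% grade 4): (0.3 × 0.695 + 0.7 × 0.293) / (0.3 × 7.02 + 0.7 × 10.14) = 0.414 / 9.204 = 0.0449 per month.
- Apparent ratio: 0.0722 / 0.0449 = 1.61.

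All settings, with the median hazard ratio from 5,000 simulated cohorts of 50 in brackets:

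| Grade 4 share | Lower-grade median | 60/40 | 70/30 |
|---|---|---|---|
| 50% | 24 months | 1.27 (1.26) | 1.61 (1.60) |
| 50% | 40 months | 1.37 (1.36) | 1.90 (1.89) |
| 70% | 24 months | 1.20 (1.19) | 1.46 (1.44) |
| 70% | 40 months | 1.27 (1.26) | 1.64 (1.59) |

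With no imbalance the ratio is 1.0. Within each grade it is 1 by construction, so a grade-stratified estimate removes the effect. A separate run with half the patients at a median of 8 months and half at 24 to 36 months gave 1.24 to 1.32 for 60/40 and 1.54 to 1.76 for 70/30.

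**3. Dilution.** Assume a hazard ratio of 2 when readout and treatment match and 1 when they do not. With matched fraction f, the pooled ratio is roughly exp(f × ln 2): 1.68 at f = 0.75, 1.41 at 0.50 and 1.19 at 0.25. The documents do not give f.

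**4. What matching can deliver.** With d events and an even split, the standard error of the log hazard ratio is about 2/√d. The 95% limits are then the estimate multiplied and divided by exp(1.96 × 2/√d): a factor of 3.45 at 10 events, 2.40 at 20 and 2.05 at 30. Detecting a hazard ratio of 0.5 with 80% power at two-sided 0.05 takes 4 × (1.96 + 0.842)² / (ln 0.5)² = 65.4, so 66 events, more than the maximum number of patients.

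**The case against.** The strongest reply is that the protocol already limits this analysis. Section 1.1 plans no formal statistical analysis of outcomes and leaves sensitivity and specificity to later studies; section 2.2 claims only to generate hypotheses. This stands as a limit on how serious the point is. It does not answer the point, because the label concerns how strong the evidence is, whereas the gap concerns which question the evidence bears on.

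Three stronger readings are tempting, and the documents do not support them.
- A reader might infer that the plan has decided to pool all patients and ignore the regimen received. Section 2.2 is silent; it neither prescribes pooling nor rules out stratification.
- A reader might infer that the study can never relate a drug's readout to response to that drug. The planned data would allow matching wherever treatment details are obtained.
- A reader might quote false-positive rates. In the simulations of step 2, an unstratified log-rank test of the uninformative marker was significant in 15 to 31% of cohorts at 70/30 and 8 to 11% at 60/40, against about 5 to 6% when stratified. The plan states no log-rank test and no alpha, so these rates do not describe a planned analysis.

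It is also fair to say that no section states that any image metric differs by grade, that the share of patients without a tested drug is not given, and that five active readouts per patient are not guaranteed. Crossing regimen, grade and surgery type in at most 50 patients would leave cells too small to use.

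**Conclusion.** The point holds as a gap in the specification with a concrete remedy. The one analysis that serves the PFS objective does not identify the readout and does not account for regimen received, grade or line, and no other section supplies this. Carried out as written, it could not separate a prognostic association from a drug-specific one.

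The size is illustrative: an apparent ratio of about 1.4 to 1.9 for a 70/30 imbalance by grade and about 1.2 to 1.4 for 60/40, with no effect of the marker within grade. These figures rest on the assumed PFS medians, grade mix and imbalance, none of which is in the documents. The dilution figures rest likewise on an assumed hazard ratio of 2 and an unknown matched fraction. Since the analysis is exploratory and unpowered, this should be corrected, but it does not threaten the primary objective, which uses no patient outcomes.

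**What to change.** Amend sections 2.2 and 7.2 as follows.
- **Matched analysis.** For patients who received a regimen that was tested ex vivo on their sample, and whose treatment data are available, relate PFS to the readout of that regimen. Name the metric in advance.
- **Grade and surgery type.** Account for grade or tumour type and for first versus relapse surgery by simple stratification or adjustment as numbers allow, without crossing all factors. Report estimates with confidence intervals, as descriptive results.
- **Patients with no tested drug.** Report them separately, using a prespecified readout such as the control culture, as a check for a purely prognostic association.
- **Labelling.** Describe any association seen only in the pooled, unmatched cohort as prognostic, not as accuracy of the assay.
- **Radiotherapy.** State that it is not in the standard ex vivo set of section 3.4, although many patients may receive it (section 5.5.9), so PFS after chemo-radiotherapy is not a pure test of a drug readout.

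The cost is wording; no new procedures or patients are needed. The price is small matched groups and wide intervals, as step 4 of the working shows. Because section 3.3 makes follow-up treatment data conditional on availability, the number of patients who could not be matched should be reported.

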## 2.3 Exploratory objectives and endpoints

Tertiary objectives	Endpoints
---------------------	-----------

Determine the rate of successfully established cultures from surgical samples	The percentage of cultures in which $\geq 70\%$ of viable tumour cells encapsulated post-isolation on day 0 are still alive on day 3 in the control cultures (no treatment) compared to the number of tumour samples ( $\geq 0.4g$ ) successfully accepted at Pear Bio's lab.
Determine the rate of successfully cultured immune cells	The percentage of cultures in which $\geq 70\%$ of viable immune cells plated post-extraction on day 0 are still alive on day 3 in the control cultures (no treatment) compared to the number of blood samples ( $\geq 40mL$ ) successfully accepted at Pear Bio's lab.
Find correlations between ex vivo tumour culture or multi-omic biomarkers and real-world patient outcomes	For any cases where patient outcomes are available or become available prospectively, such as recurrence post-surgery, potential predictive or prognostic biomarkers will be identified. As this data will be sparse, the analysis will only be used to generate hypotheses for future trials, if the data allows.
Assess Pear Bio's assay ability to categorise patients for below average or above average overall survival (OS)	
Patient data is collected up to death and their time from diagnosis to death is recorded to determine the overall survival (OS) time.
 
This analysis will use median OS within the study cohort to differentiate patients as generally responsive or resistant to treatment. The analysis will then explore indicators/biomarkers in Pear Bio's test that can identify patients as generally responsive or resistant to treatment, agnostic of the therapeutic choice.

Assess the correlation of omics biomarkers to patient PFS, ORR and/or OS	
Omics readouts taken of patient tumour samples at Pear Bio's laboratory will be used to determine whether any biomarkers can correlate to therapeutic response.
 
Omics methods include:
 
 
1. Immunofluorescence (IF)
 
2. RNASeq
 
3. Tumour mutational burden (TMB) and microsatellite instability (MSI)
 
 
Prediction methods include:
 
 
1. Correlating baseline expression of biomarkers in the tumour sample to real-world patient outcomes
 
2. Comparing the change in biomarker expression after ex vivo treatment testing to real-world patient outcomes
 

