## 1: INTRODUCTION

### 1.1 Trial outline

Pear Bio have developed a 3D micro-tumour and computer vision platform to culture patient-derived tumour samples and predict sensitivity to various therapeutic agents. This study is intended to validate the mechanism of action of FDA-approved primary brain tumour therapies, such as Temozolomide, Lomustine and Bevacizumab, as well as therapies being assessed in clinical trials, on fresh brain tumours and autologous immune cells isolated from whole blood.

This is a proof of concept study to confirm that therapies used in primary brain tumours can be tested in Pear Bio's platform. Follow-on studies will be used to determine the sensitivity and specificity of Pear Bio's test in predicting patient response (OS and PFS). This study will acquire fresh patient tumour samples and 40 mL of whole blood per patient. Samples will be shipped fresh on the same day of collection to Pear Bio's lab. Histopathology reports will be provided to Pear Bio shortly after the sample shipment in order to confirm the tumour subtype (although samples will not be excluded from analysis based on tumour subtype). Other available patient data, including imaging and imaging reports, will also be provided in a pseudonymised form. Patients who have had previous tissue sampling (i.e. those undergoing treatment for relapsed disease) will also provide information on previous histology and treatment.

Pear Bio will isolate cells from the tumour samples and whole blood, co-culture them into 3D micro-tumours, and run live microscopy-based assays to determine *ex vivo* tumour response to treatments. Image data will be analysed using a proprietary computer vision pipeline to measure *ex vivo* tumour response metrics, such as tumour cell death, tumour cell migration and immune cell infiltration. Molecular biology assays will be conducted to determine changes in DNA features (tumour mutational burden and mis-match repair), gene expression (PCR or RNASeq) and protein distribution (immunofluorescence or spatial proteomics assays) for biomarkers due to *ex vivo* treatment exposure.

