#### 3.1 Overall design

PEAR-GLIO Protocol v1.0  
3rd March 2023

This is a UK-based, observational study that aims to validate a diagnostic tool on its ability to test therapeutic sensitivity of primary solid brain tumours *ex vivo*. Patients diagnosed with a brain tumour on imaging, or who have had previous treatment for a brain tumour and are now undergoing further surgery as clinically indicated, will undergo standard of care surgery, and have 40mL of whole blood collected. The material available from the surgical sample for this study will be shipped fresh alongside whole blood to Pear Bio. The patient will go through routine post-surgical care and data collection. Any previous or subsequent treatments and events occurring post-surgery, such as the administration of adjuvant therapy or recurrence, will be recorded and communicated to Pear Bio. The samples and data sent to Pear Bio will be used to evaluate the study's objectives.

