**Table 1: Schedule of assessments**

Table notes:

1. A redacted histopathology report will be sent to Pear Bio when it is ready (i.e., it does not have to be sent alongside the tissue, blood and other available data from the day of the surgery).
2. Available data is transferred alongside the tumour sample within 24 hours of surgery to Pear Bio's laboratory. Any remaining data will be transferred as soon as feasible, and we will transfer any further imaging at a single timepoint at 12 months after surgery
3. Relating only to research procedures (e.g., taking a volume of blood that is beyond standard care for a given patient). This can be conducted by telephone – physical examination to be done only if clinically indicated.
4. Collected only if available for consenting patients within the study period.
5. Collected only if available for consenting patients within the study period.

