## 5.5 Procedures and measurements

### 5.5.1 Demographics and medical history

Demographic data collected will include age, sex and race/ethnicity. Details of medical history obtained as part of standard of care will be collected, including details of any relevant medical conditions occurring prior to consent.

Details will also be collected on the patient's cancer diagnosis, including site, date of diagnosis, and tumour size.

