## **7.4 End of study definition**

The end of the trial is defined as the last patient's last data at a maximum of 12 months post-surgery (outstanding data sent to Pear Bio or final laboratory readout, whichever happens later). In cases of early termination of the trial (e.g., due to slow accrual) or a temporary halt, the Sponsor will notify the REC within 15 days of the decision, and a detailed written explanation for the termination/halt will be given.

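### Exploratory OS label: timing from diagnosis and splitting at the whole-cohort median mixes re-operation status and tumour grade with treatment response, and no censoring rule is given (minor)

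*Combined protocol and SAP*

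**What the plan says.** Section 2.3 defines OS for an exploratory objective: "Patient data is collected up to death and their time from diagnosis to death is recorded". It then sets the cut: "This analysis will use median OS within the study cohort to differentiate patients as generally responsive or resistant to treatment". Assay indicators are explored against that label, whatever therapy the patient received. The cut has no split by line of treatment, tumour type or grade.

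Section 3.1 admits newly imaged tumours and also patients "or who have had previous treatment for a brain tumour and are now undergoing further surgery as clinically indicated". Section 1.1 confirms that patients with relapsed disease take part and supply their earlier histology and treatment. Section 4.1 admits grades 1 to 4 (grades 2 to 3 for meningioma). Section 5.5.1 collects details of the "cancer diagnosis, including site, date of diagnosis, and tumour size" but does not say whether a relapsed patient's date is that of first diagnosis or of recurrence. Section 2.2 plans curves by line of treatment, where feasible, for progression-free survival (PFS) only.

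On follow-up, section 7.4 states: "The end of the trial is defined as the last patient's last data at a maximum of 12 months post-surgery". Section 7.5 says missing data are not imputed. Section 7.2.3 describes no OS method and no censoring rule.

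**The concern.** A re-operated patient must have lived from first diagnosis to the study operation to be enrolled. On the ordinary reading of diagnosis, that guaranteed time is part of OS although it elapsed before the sampled tissue was taken. It cannot reflect how that tissue responds to later treatment, yet it moves the patient toward the responsive half. Lower-grade patients are also likelier to fall in that half for reasons other than drug sensitivity.

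The label is the target for the search. An assay readout that only tells re-operated from new tumours, or low from high grade, could look informative about treatment response and be carried into a later trial as a hypothesis.

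The second problem is that a patient alive at the data cut, with less observed time than the cohort median, belongs to neither half. The plan does not say what happens to that patient.

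**Working it through.** The plan has no figure to reproduce: the maximum of 50 patients (section 7.1) has no power or event calculation behind it.

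**Inputs from the documents.** Glioblastoma (GBM) median survival 15 months (section 1.2.2); up to 50 patients (section 7.1); grades 1 to 4 eligible (section 4.1); study end at most 12 months after the last patient's surgery (section 7.4).

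**Assumptions, not in the documents.** 30% re-operated (15 of 50); lead L from diagnosis to study surgery of 6, 12 or 24 months for re-operated patients and zero for new ones; exponential survival after surgery; the 15-month median applied from surgery; everyone followed to death in steps 1 to 4.

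**Step 1. All GBM, equal post-surgery survival.** The pooled median m solves 0.7·2^(−m/15) + 0.3·2^(−(m−L)/15) = 0.5. So the responsive share among new patients is 0.5/(0.7 + 0.3·2^(L/15)), and among re-operated patients it is that value times 2^(L/15).

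- L = 6: 2^0.4 = 1.320; 0.5/1.096 = 0.456; re-operated 0.602
- L = 12: 2^0.8 = 1.741; 0.5/1.222 = 0.409; re-operated 0.712
- L = 24: 2^1.6 = 3.031; 0.5/1.609 = 0.311; re-operated 0.942

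Timed from surgery (L = 0), both are 0.50.

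**Step 2. Add a grade mix.** Let 30% of the cohort be lower-grade new patients with an assumed 60-month median, 40% new GBM and 30% re-operated. With x = 2^(−m/60), solve (0.4 + 0.3·2^(L/15))·x⁴ + 0.3·x = 0.5. The re-operated share is x⁴·2^(L/15); the new share is (0.4·x⁴ + 0.3·x)/0.7.

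| Lead (months) | Step 1: re-operated v new | x | Step 2: re-operated v new |
|---|---|---|---|
| 6 | 60% v 46% | 0.764 | 45% v 52% |
| 12 | 71% v 41% | 0.741 | 52% v 49% |
| 24 | 94% v 31% | 0.688 | 68% v 42% |

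The same rule favours re-operated patients, is close to neutral, or favours new patients, depending on case mix and lead.

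**Step 3. Does changing the time origin suffice?** Take all GBM with an assumed 9-month median after re-operation. At L = 6, the equation 0.7·2^(−m/15) + 0.3·2^(−(m−6)/9) = 0.5 is solved by m = 15, so the diagnosis clock gives 50% v 50%. Timed from surgery (L = 0), m = 12.8 and the split is 37% v 55%. The diagnosis clock happens to balance here and the surgery clock does not, because the groups differ in prognosis.

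**Step 4. Effect on a search for indicators (illustration only).** Simulate cohorts of 50 with a readout unrelated to survival within each group but 1 SD higher in re-operated tumours, and t-test it against the label. The plan specifies no such test, and nothing in the documents supports a 1 SD difference. The rate of p<0.05 with 15-month medians is 6.9%, 13.5% and 39.0% at leads of 6, 12 and 24 months if all are GBM, and about 6%, 5% and 12% with the grade mix. Timed from surgery without stratification, with a 9-month re-operated median, it is about 8%, or about 16% with the grade mix. Adjusted for new versus re-operated status, it stays near 5% in every scenario. That last result follows from the set-up, in which the readout varies with re-operation status only; a readout that also tracks grade would need grade as well.

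**Step 5. Follow-up.** The last patient enrolled is followed for at most 12 months. With a 15-month median, the chance of being alive then is 2^(−12/15) = 0.574. Death cannot be observed for every patient, so section 2.3 needs a censoring rule. Section 7.5 does not supply one: declining to impute does not say whether a living patient is dropped, censored or labelled.

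**The case against.** The strongest objection is scope. Section 1.1 rules out formal statistics on patient outcomes because patients are varied and few. Section 2.3 makes the OS objective exploratory, section 7.2.3 confines outcome correlations to generating hypotheses, and section 7.2.1 keeps outcomes out of the primary analysis. This stands and is why the point is minor. It does not remove the point, because an informal search against a mixed label still yields misdirected hypotheses.

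The direction and size are also open. A reader might infer that re-operated patients will be over-labelled as responsive. The documents give neither the re-operated share nor the lead time, and step 2 shows that the effect can vanish or reverse. If date of diagnosis means the recurrence, most of the lead time disappears.

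A reader might take the 39.0% as the plan's false-positive rate. It is not: it belongs to an unplanned test and an assumed readout difference.

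On follow-up, a reader might infer that every patient is cut at 12 months, so that the median is rarely reached; under that reading and a 15-month median, the chance of at least 25 deaths in 50 would be 0.18. But the limit in section 7.4 concerns the last patient, and earlier patients may be followed longer. Nor is follow-up unmentioned, since sections 2.3 and 7.4 both address it. The Table 1 notes limiting collection to available data concern recurrence and further therapy, not survival status. What remains is that no data cut-off for earlier patients and no rule for living patients is given.

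**Conclusion.** The concern holds as a minor point. As written, and unless diagnosis means recurrence, the label counts survival before the sample existed and mixes re-operation status and grade with treatment response. Under the stated assumptions the gap between re-operated and new patients runs from 63 percentage points in favour of re-operated (94% v 31%) to 7 points the other way (45% v 52%). These figures show a range, not an estimate. The time origin is only part of the problem; the missing stratification matters more, since timing from surgery alone can leave the groups as far apart as 37% v 55%.

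The follow-up statements leave a gap for patients alive at study end. They do not conflict for every patient, and the documents do not show that the median will be unreachable. The primary objective is unaffected.

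**What to change.** 1. Main change: explore indicators within new and re-operated patients separately, or stratified by or adjusted for that status. Add tumour type or grade as a second factor only if numbers allow.
2. Together with this, not instead of it, time OS from study surgery. Alternatively keep diagnosis, defined as first diagnosis, with delayed entry at study surgery; this works only in a time-to-event comparison, because delayed entry cannot be built into an individual's label.
3. Treat patients alive at last contact as censored, and give no responsive or resistant label to those censored before the median.
4. Reconcile sections 2.3 and 7.4 on follow-up, state the data cut-off, and confirm that dates of death and last contact are captured. Table 1 has no explicit row for them, and the case report form is not among the documents.

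The cost is small. Diagnosis date and previous treatment are already collected. With full follow-up and 15 of 50 re-operated, splitting within groups (17 v 18 and 7 v 8) gives a standard error for a standardised difference of 1/√(17·18/35 + 7·8/15) = 0.2831, against 1/√(25·25/50) = 0.2828 for a pooled 25 v 25. Precision is low either way and falls further with censoring. The rest is some extra analysis work.
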